1. INTRODUCTION

This Phase 2a open-label, non-randomized U.S. multicenter study is designed to evaluate the safety and efficacy of ibrutinib monotherapy and in combination with low dose cytosine arabinoside (LD-AraC) or azacitidine in the treatment of subjects with Acute Myeloid Leukemia (AML).

This statistical analysis plan (SAP) describes the statistical methodology of efficacy and safety for this study. This plan does not cover the pharmacokinetic (PK) or biomarker analyses. These analyses will be performed and reported by the DMPK Department and Biomarker group of Pharmacyclics, respectively.

1.1. Study Objectives

The primary objectives are to evaluate the efficacy of ibrutinib monotherapy or in combination with either LD-AraC or azacitidine in the treatment of AML using the overall remission rate (ORR, defined as the proportion of subjects achieving a complete remission (CR) or complete remission with incomplete marrow recovery (CRI)) according to the LeukemiaNet guidelines ([Döhner 2010, Appendix 6 in Protocol Amendment 1.0](#)) and to evaluate the safety and tolerability of ibrutinib monotherapy or in combination with either LD-AraC or azacitidine in subjects with AML.

The secondary objectives are to evaluate clinical efficacy by assessing relapse-free survival (RFS), event-free survival (EFS) and overall survival (OS) and to evaluate clinical benefit defined as CR, CRI, morphologic leukemia-free state, and partial remission (PR).

The exploratory objectives are to determine the PK of ibrutinib monotherapy or in combination with either LD-AraC or azacitidine in an AML population and to evaluate prognostic and predictive biomarkers relative to treatment outcomes (ie, BTK/pBTK, secreted proteins, gene expression profiling, mutational analysis). Exploratory objectives are outside the scope of this SAP.

1.2. Study Endpoints

Response criteria from the LeukemiaNet guidelines have been used by all investigators to assess efficacy outcomes. In accordance with the study protocol, the primary efficacy endpoint is defined as the ORR per investigator assessment of ibrutinib monotherapy and in combination with LD-AraC or azacitidine, respectively. The secondary efficacy endpoints include RFS for subjects who achieve a CR or CRI; EFS; OS and Clinical Benefit Rate (CBR; defined as the proportion of subjects achieving CR, CRI, morphologic leukemia-free state, or PR). Safety endpoints include the safety and tolerability of ibrutinib monotherapy and in combination with LD-AraC or azacytidine.

 An AbbVie Company	PCYC-1131-CA Statistical Analysis Plan	Page 4 of 7
--	---	-------------

1.3. Study Design

A maximum of 101 subjects will be enrolled in 3 treatment cohorts.

- Cohort 1 – ibrutinib monotherapy: ibrutinib 560 mg once daily on a continuous basis. Up to 33 response evaluable subjects
- Cohort 2 – ibrutinib + LD-AraC: ibrutinib 560 mg once daily on a continuous basis plus low dose cytarabine. Up to 34 response evaluable subjects
- Cohort 3 – ibrutinib + azacitidine: ibrutinib 560 mg once daily on a continuous basis plus IV azacitidine. Up to 34 response evaluable subjects

The study will begin with safety run-in phase in Cohort 2 only. Six subjects will receive ibrutinib at a dose level of 560 mg once daily on a continuing basis starting 2 days prior to the first cytarabine dose. Assessment for dose limiting toxicities (DLTs) will continue for the first treatment cycle. If 2 of the first 6 subjects experience DLT(s), 3 additional subjects will be assessed for DLT(s). If 3 or more of the 9 subjects experience DLT(s), enrollment will be halted at the 560 mg dose level. At sponsor's discretion, a dose of 420 mg ibrutinib or lower (plus LD-AraC) may be explored. If less than 2 out of 6 subjects or less than 3 out of 9 subjects experience DLT(s), additional subjects will be enrolled in Cohort 1 or 2 at the discretion of the investigator. Efficacy parameters will be monitored closely. In the event response assessments suggest futility in the ibrutinib + AraC cohort, further enrollment in either cohort 1 or 2 will be closed and a new cohort of ibrutinib + azacitidine will be started. For Cohort 3 the same safety run-in principle as Cohort 2 (6+3 design) will be implemented. Study treatment will continue in subjects who demonstrate a PR or better on their Cycle 2 Day 1 bone marrow assessment according to the LeukemiaNet guidelines or based on clinical benefit as determined by the treating physician. Treatment may continue thereafter until unacceptable toxicity, treatment failure (TF), or withdrawal of consent. Subjects treated in the ibrutinib monotherapy cohort who experience a documented TF or relapse will be permitted to add LD-AraC to ibrutinib per investigator discretion.

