5. SAFETY

Adverse events, changes in clinical laboratory results from baseline, summary of vital signs and ECG values will be provided. All safety analyses will be based on all treated population (except for DLT evaluation which will be based on DLT population).

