5.2.1. Treatment-emergent Adverse Events

Treatment-emergent adverse events will be summarized by system organ class and preferred terms and by NCI toxicity grade. The same summary will be provided for treatment-related AEs, AEs leading to treatment discontinuation, AEs leading to treatment discontinuation for subjects who discontinued treatment due to AE, AEs leading to dose reduction and serious TEAEs. Adverse event overview on the incidences of all the above will be presented.

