5.2.3. Other Malignancies

Other malignancies are defined as new malignant tumors including categories non-melanoma skin cancer, melanoma skin cancer and other non-skin cancers. Both treatment-emergent adverse events of other malignancies and all other malignancies AEs reported during the study will be summarized.

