5.3. Clinical Laboratory Tests

All gradable laboratory parameters will be graded using the NCI CTCAE version 4.03. A summary of worst post-baseline toxicity grade will be provided. The events with Grade 3 and 4 as the worst post-baseline toxicity grade will be also provided. Only subjects whose grades worsened are counted in the numerator of percentage calculation while the denominator is all subjects in each treatment cohort all treated population. Liver function abnormality by Hy's law will be summarized. Listing of white blood cell (WBC) count, platelet count, blood blasts (%) and abnormal cells will be presented.

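### The Cohort 1 worst-grade laboratory table has no split at first LD-AraC dose, so grades first reached on ibrutinib plus LD-AraC count under the monotherapy cohort (minor)

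*SAP*

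**What the plan says.** Section 1.3 defines Cohort 1 as ibrutinib alone, with up to 33 response evaluable subjects. It then states that subjects in this cohort who have a documented treatment failure or relapse "will be permitted to add LD-AraC to ibrutinib per investigator discretion".

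Section 5.3 sets the laboratory rule in four parts:

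- The main display is worded as follows: "A summary of worst post-baseline toxicity grade will be provided".
- High grades get a display of their own: "The events with Grade 3 and 4 as the worst post-baseline toxicity grade will be also provided".
- On who enters the numerator, the rule is "Only subjects whose grades worsened are counted in the numerator of percentage calculation".
- On what that count is divided by, it reads "while the denominator is all subjects in each treatment cohort all treated population".

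The layout by cohort is thus explicit. The window has a start (baseline) but no stated end, and a change of regimen is not mentioned.

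Section 5 says "All safety analyses will be based on all treated population", with DLT evaluation as the only exception. Section 2.1 defines that population by cohort, from at least one dose, with no rule for subjects whose regimen changes. Sections 1.1 and 1.2 list the safety of ibrutinib monotherapy and of the combinations as separate targets.

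**The concern.** From the date of the add-on, a Cohort 1 subject receives the two drugs that define Cohort 2 but stays in Cohort 1 for the laboratory table. A reader will take the Cohort 1 column as the laboratory safety of ibrutinib alone, and for such subjects it may not be.

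Section 4.1 cancels every efficacy endpoint except overall survival, so safety is one of the few summarised results left for this cohort. The SAP also commits to no count of add-on subjects and no time of add-on. Section 3 lists disposition, concomitant medications and exposure to ibrutinib. These might reveal the add-on, but the text does not say that they will. A reader could not tell whether the mixing was absent, slight or substantial.

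**Working it through.** **Inputs.** From the SAP: the add-on permission and the Cohort 1 maximum of 33 response evaluable subjects (section 1.3), and the laboratory numerator and denominator (section 5.3). The SAP gives no number of add-on subjects, no laboratory event rates and no all treated n for Cohort 1, so it holds no figure of its own to reproduce. Everything below beyond n = 33 is an assumption and is marked as such.

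**Step 1: does the rule count add-on grades?** Take a Cohort 1 subject who adds LD-AraC and then has a first worsening, or a first Grade 3 or 4 value.

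- The value is after baseline, so it is inside the section 5.3 window.
- The subject's grade has worsened, so the subject is in the numerator.
- The subject is in the Cohort 1 all treated population, so the event is divided by the Cohort 1 total.

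No other section of the SAP removes it.

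**Step 2: direction.** A worst grade is a maximum over the window. Lengthening the window can raise a subject's worst grade or leave it unchanged, but never lower it. Compared with a window that ends before the add-on, the full window gives an equal or higher Cohort 1 percentage. A subject who had already reached the counted grade on ibrutinib alone changes nothing.

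**Step 3: size per subject.** With k affected subjects the shift is k/n.

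| n | Source | Shift for k = 1 |
|---|---|---|
| 33 | section 1.3, response evaluable maximum; all treated n may differ | 1/33 = 3.0 points |
| 20 | assumed, after early termination | 1/20 = 5.0 points |
| 10 | assumed, after early termination | 1/10 = 10.0 points |

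At n = 33, k = 0 gives 0, k = 2 gives 2/33 = 6.1 points, and k = 3 gives 3/33 = 9.1 points.

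**Step 4: illustration with assumed counts.** Suppose 10 of 33 subjects have the event before any add-on and 3 more have it first afterwards. Exact (Clopper-Pearson) 95% intervals are:

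- window ending before the add-on: 10/33 = 30.3% (15.6 to 48.7), half-width 16.6 from unrounded limits;
- full window: 13/33 = 39.4% (22.9 to 57.9).

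The shift of 39.4 - 30.3 = 9.1 points is smaller than the half-width. The interval describes sampling error, however, and does not allow for events attributed to the wrong regimen.

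**Step 5: do the adverse event tables share the problem?** Section 5.2.1 says "Treatment-emergent adverse events will be summarized by system organ class and preferred terms and by NCI toxicity grade". It states no layout by cohort, and the SAP does not define the treatment-emergent window. Section 5.2.3 says "all other malignancies AEs reported during the study will be summarized", which would include an add-on period, but again no layout by cohort is stated. The problem is therefore shown for the laboratory table and is only conditional for adverse events.

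**The case against.** The strongest reply is that section 5.3 is coherent as a summary by enrolled cohort. The add-on is a permitted part of the Cohort 1 course, ibrutinib continues through it, and the section does not call its result a monotherapy-only rate. Counting every grade after baseline is an inclusive and defensible safety summary. This stands, and it is why the full table should be kept. It does not remove the need to show the monotherapy period as well, because sections 1.1 and 1.2 make that a separate target.

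A second objection is that a cut at the add-on is driven by outcome: it falls only in subjects with treatment failure or relapse, and it drops their later ibrutinib exposure while keeping them in the denominator. Late ibrutinib toxicity could then be understated. This also stands, and it rules out replacing the full table with the cut one.

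A third is that the protocol, not shown here, may define an on-treatment window. It may, but section 5.3 states its own rule and points to no such window.

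Finally, section 5.3 plans listings of white cells, platelets, blasts and abnormal cells, and section 2.2 allows further listings on request. These could help with haematology, but neither promises the LD-AraC start date. The statement in section 2.1 that there will be no subgroup analysis does not forbid a split by time period, so it does not bear on the point either way.

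A reader might infer more than the SAP supports: that the Cohort 1 table is known to be materially inflated, that all adverse event tables are affected, or that the extra grades measure LD-AraC toxicity. The SAP gives no add-on count. It leaves the layout and window of the adverse event tables open. Grades reached after treatment failure or relapse may reflect progressing AML.

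**Conclusion.** The point holds for the laboratory table. Read together, sections 1.3 and 5.3 count a grade first reached on ibrutinib plus LD-AraC in the monotherapy cohort, and nothing else in the SAP separates it.

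The actual size is unknown. It depends on how many Cohort 1 subjects added LD-AraC and then first reached the counted grade, and on the all treated n, none of which the SAP gives; the figures above other than 1/33 rest on assumed counts. The study stopped for lack of efficacy and treatment failure is one of the triggers for the add-on, so use of the permission is plausible, but the SAP does not say that it was used.

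Severity is minor: the tables are descriptive, no test depends on them, and a labelled supplement resolves the matter.

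**What to change.** In section 5.3, for Cohort 1:

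1. Keep the table of worst grade over all post-baseline data, and label it as including any LD-AraC add-on period.
2. Add a table of worst grade from first ibrutinib dose through the day before first LD-AraC dose, or to the usual end of the window for subjects without an add-on. Show add-on-period grades separately.
3. Report the number of subjects who added LD-AraC and the time from first ibrutinib dose to first LD-AraC dose. If the number is zero, one sentence saying so replaces item 2.
4. Apply the same split to adverse event summaries, including other malignancies, only where they are laid out by cohort and their window runs past the add-on.

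A footnote should say that the cut date is triggered by treatment failure or relapse, that the pre-add-on table therefore has shorter, outcome-dependent follow-up for those subjects and omits their later ibrutinib exposure, and that grades after the add-on may reflect progressing AML and are not a measure of LD-AraC toxicity.

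The cost is a few lines of SAP text, one date flag in programming and one small extra table. The change is to the analysis only and leaves the rule that permits the add-on as it is.

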1.4. Sample Size Considerations

The sample size of 6 or 9 safety run-in subjects for safety review was based on clinical experience and conventional DLT studies. The total sample size was calculated to detect a meaningful signal of activity of each treatment regimen while minimizing risk of continuing enrollment under null conditions. The sample size was estimated for each treatment cohort without multiplicity adjustment. The study will enroll approximately 101 subjects in total, including 33 response evaluable subjects for monotherapy and 34 response evaluable subjects for each combo therapy. The sample size of 33 subjects was calculated to test the null hypothesis that the ORR of ibrutinib monotherapy is $\leq 5\%$ (not clinically compelling) versus the alternative hypothesis that ORR will be $\geq 20\%$, with a significance level of 5%, and 80% power. The sample size of 34 subjects was calculated to test the null hypothesis that the ORR of ibrutinib plus LD-AraC or ibrutinib plus azacitidine is $\leq 15\%$ (not clinically compelling) versus the alternative hypothesis that ORR will be $\geq 35\%$, with a significance level of 5%, and 80% power.

 An AbbVie Company	PCYC-1131-CA Statistical Analysis Plan	Page 5 of 7
--	---	-------------

2. GENERAL ANALYSIS CONSIDERATION

2.1. Analysis Population s

All treated population includes all enrolled subjects who received at least 1 dose of study drug in each study cohort. The DLT population will include the first 6 to 9 safety run-in subjects who signed the informed consent form and were enrolled for the safety run-in period, and were evaluable for DLT. The DLT population will be used to summarize dose limiting toxicities in the first 6 to 9 subjects in the safety run-in period. No subgroup analysis will be performed.

2.2. Analysis Convention s

Descriptive statistics (mean, standard deviation or standard error, median, minimum, and maximum) will be used to summarize continuous variables. Categorical variables will be summarized by counts and percentages. Unless otherwise specified, exact 95% confidence intervals will be constructed for event rates or response rates. As appropriate, data collected on the electronic case report form (eCRF) will be presented in data listings upon request. All statistical analyses will be performed using SAS® version 9.2 or later.

3. SUBJECT INFORMATION

All analyses in this section will be based on the all treated population for each treatment cohort unless otherwise specified, including subject disposition, demographics and baseline characteristics, baseline disease characteristics, prior AML therapies, concomitant medications including CYP3A inhibitors, and exposure to ibrutinib.

3.1. Protocol Deviations

In general, protocol violations/deviations will be reviewed by the study team during the study, and important protocol deviations will be determined based on the review. The information on important protocol deviations will be generated based on the review outcome for all subjects by the clinical team.

4. EFFICACY

4.1. Change from Protocol-defined Analysis

The study was terminated early due to lack of efficacy. As such, none of the protocol-defined efficacy endpoints including primary efficacy endpoints and secondary efficacy endpoints listed in [Sections 1.2](#) will be calculated except for OS. A subject listing with all the available response assessment data for all treated patients will be provided. Overall survival will be analyzed as described in [Section 4.2](#).

 An AbbVie Company	PCYC-1131-CA Statistical Analysis Plan	Page 6 of 7
--	---	-------------

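### SAP Section 4.1 replaces the primary efficacy endpoint (ORR) and CBR with a listing; early termination does not rule out a descriptive rate with an exact interval

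*SAP*

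**What the plan says.** Section 1.2 states that "the primary efficacy endpoint is defined as the ORR per investigator assessment" for each regimen. It makes clinical benefit rate (CBR: CR, CRI, morphologic leukemia-free state or PR) a secondary endpoint, alongside RFS, EFS and OS. Section 1.4 sizes every cohort on ORR, "including 33 response evaluable subjects for monotherapy and 34 response evaluable subjects for each combo therapy", with null and target rates of 5% and 20% for monotherapy and 15% and 35% for each combination.

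Section 4.1 then changes the plan. The reason given is that "The study was terminated early due to lack of efficacy". On that ground "none of the protocol-defined efficacy endpoints including primary efficacy endpoints and secondary efficacy endpoints listed in" Section 1.2 will be calculated, with OS the single exception. In place of the rates, "A subject listing with all the available response assessment data for all treated patients will be provided".

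Three other places bear on the point:

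- Section 2.1 defines an all treated population in each cohort.
- Section 2.2 sets exact 95% confidence intervals as the default for response rates, unless another rule is specified.
- Section 4.2 keeps a Kaplan-Meier analysis of OS, with a median, its interval and landmark estimates.

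**The concern.** The reason given in Section 4.1 does not lead to the decision taken. Stopping early can leave the planned test without its planned sample size. With few responders it can also make RFS, which is defined only in responders, uninformative; dropping EFS is likewise defensible. None of this prevents counting responders over a known denominator.

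ORR is the endpoint on which the study was built: "The total sample size was calculated to detect a meaningful signal of activity of each treatment regimen", and ORR carries the only null and target rates in the SAP. OS, the only efficacy result that remains, has no reference value in the document. A reader of the final analysis would therefore have no planned estimate or interval to set against the 20% or 35% target. Anyone who computed a rate from the listing would have to choose the rules alone, chiefly how to count subjects without a response assessment. In Cohort 1 there is a further choice, because subjects with treatment failure or relapse "will be permitted to add LD-AraC to ibrutinib per investigator discretion".

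**Working it through.** **1. Are the cohort sizes driven by ORR?** Inputs from Section 1.4: N = 33, 5% vs 20%; N = 34, 15% vs 35%; significance level 5% (sidedness not stated); power 80%. Let X be the number of responders, binomial (N, p). Find the smallest N for which some cut-off r gives P(X ≥ r | null) ≤ 0.025 and P(X ≥ r | target) ≥ 0.80.

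- Monotherapy: N = 33, r = 5. P(X ≥ 5 | 5%) = 0.0230; P(X ≥ 5 | 20%) = 0.818.
- Each combination: N = 34, r = 10. P(X ≥ 10 | 15%) = 0.0240; P(X ≥ 10 | 35%) = 0.804.

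Both stated sizes are reproduced as the exact minimum for a two-sided 5% test, and 33 + 34 + 34 = 101 matches the stated total. An upper-tail level of 0.05 would give 27 and 28. The sizes are therefore exact-binomial sizes on ORR.

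**2. Does the SAP supply what a descriptive rate needs?**

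- Numerator: investigator response assessments, which Section 4.1 will list.
- Denominator: the all treated population per cohort, Section 2.1. The listing covers the same subjects.
- Interval: exact 95%, Section 2.2.

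Nothing has to be collected. An exact interval exists at any n, including with no responders.

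**3. What would the interval show?** The SAP gives no final n or responder counts, so the counts below are assumed. The Clopper-Pearson 95% upper limit for x responders out of n is the 0.975 quantile of Beta(x + 1, n − x). For x = 0 it reduces to 1 − 0.025^(1/n).

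| Assumed x/n | Exact 95% upper limit | Target ORR | Target excluded? |
|---|---|---|---|
| 0/6 | 1 − 0.025^(1/6) = 45.9% | 35% (combination) | no |
| 0/9 | 1 − 0.025^(1/9) = 33.6% | 35% (combination) | yes |
| 0/16 | 1 − 0.025^(1/16) = 20.6% | 20% (monotherapy) | no |
| 0/17 | 1 − 0.025^(1/17) = 19.5% | 20% (monotherapy) | yes |

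Even with no responders, whether the target is excluded depends on n.

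**4. Does the denominator matter?** Suppose six combination subjects were assessed with no response, and three more were treated but never assessed. Over assessed subjects the upper limit is 45.9% (0/6). Counting the three as non-responders gives 33.6% (0/9), which falls below 35% with no added response information. The denominator rule should be fixed and the number unassessed should be shown.

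**The case against.** The strongest defence is that the change is open. It stands under a heading that announces a departure from the protocol, gives a reason, and keeps all the response data in the listing. A reader can count responders and compute an interval, so the information is unsummarised rather than lost. Safety, the other primary objective, is still analysed in full. A rate from a stopped study may be imprecise and, because stopping was for lack of efficacy, biased downward. All of this stands. It limits the weight of the point and calls for a caveat on the rate, but it does not explain why the rate is omitted. The plan accepts similar imprecision for the OS median and its interval in the same subjects.

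Three stronger readings are tempting but unsupported:

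- *The SAP contradicts itself.* It does not. The interval rule in Section 2.2 allows exceptions, and Section 4.1 specifies one.
- *Each cohort fell short of its target.* The SAP gives no responder counts and does not say which cohorts enrolled. Under Section 1.3, Cohort 3 opens only if Cohort 2 looks futile.
- *The decision to stop rested on ORR, and its basis is now missing.* Section 4.1 does not say what lack of efficacy was measured on. The only futility provision, "In the event response assessments suggest futility in the ibrutinib + AraC cohort", concerns Cohort 2 and leads to a new cohort, not to ending the study.

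The absence of a reference value for OS is no fault in itself, since a single-arm study may describe survival. It matters only because OS is the sole efficacy estimate left.

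**Conclusion.** The point holds as a poorly justified analysis choice. Early termination for lack of efficacy supports dropping the hypothesis tests, and RFS and EFS, but not a descriptive ORR and CBR. As written, the primary efficacy objective receives no estimate and no interval.

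The size of the effect on the trial's conclusion is unknown, because final enrolment, the cohorts opened and the responder counts are not in the SAP. The 0/6, 0/9, 0/16 and 0/17 figures rest on assumed counts. They show only that an interval can be informative and that its reading depends on n; a reader might infer from them that this trial's conclusion is weak, but they do not show that. This is a cheap improvement.

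**What to change.** Amend Section 4.1 along these lines:

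> For each cohort that enrolled subjects, ORR (CR + CRI) and CBR per investigator assessment will be reported as responders/n with exact (Clopper-Pearson) 95% confidence intervals over all treated subjects. Subjects without a post-baseline response assessment count as non-responders, and their number will be shown. If the protocol defines a response evaluable set, the rates in that set will also be shown. In Cohort 1, any response first seen after LD-AraC was added will be identified and not attributed to monotherapy. The estimates are descriptive and no hypothesis test will be done. Because the study stopped early for lack of efficacy, the rates may be biased downward and the intervals may not keep nominal coverage.

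The second denominator is there because counting unassessed subjects as non-responders lowers the upper limit and can make a target look excluded. It should follow the protocol's own definition rather than a new one, since Sections 1.3 and 1.4 of the SAP use the term response evaluable without defining it. Keep the listing and the OS analysis; RFS and EFS may stay cancelled.

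The cost is a paragraph of SAP text and one small table per enrolled cohort, with no new data. The downside is that the estimates may be imprecise and can be read only descriptively.
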